6 INTRODUCTION

Generalized anxiety disorder (GAD) is one of the most frequently occurring childhood anxiety disorders¹. In the United States, an estimated 2.2% of adolescents (aged 13 through 18 years) had GAD, with an estimated 0.9% having severe impairment based on data published in 2010. The prevalence of GAD among adolescents was higher for females (3.0%) than for males (1.5%)².

An anxiety disorder such as GAD in children and adolescents increases the risk for substance abuse and suicidal ideation and suicide attempts, and also increases the risk for anxiety or depressive disorders in adulthood^{3,4,5}. However, anxiety disorders are often untreated in children and adolescents⁶.

There is increasing evidence to suggest that selective serotonin reuptake inhibitors (SSRIs) are effective treatments for youth with GAD and are generally well tolerated⁷.

Escitalopram, the S-enantiomer of racemic citalopram, is an SSRI primarily responsible for the serotonin reuptake inhibition produced by citalopram. Escitalopram binds preferentially to the serotonin transporter and has very low or no affinity for neurotransmitter receptors or for the dopamine and norepinephrine transporters. The mechanism of antidepressant action of escitalopram is presumed to be linked to potentiation of serotonergic activity in the central nervous system resulting from its inhibition of central nervous system neuronal reuptake of serotonin (5-hydroxytryptamine).

Five clinical studies evaluating the efficacy and safety of escitalopram in adult patients with GAD have been completed. Three of the 5 studies were placebo-controlled; one was an open-label extension study; and one was a relapse-prevention study. The efficacy of escitalopram in the acute treatment of GAD was demonstrated in the three, 8-week, flexible-dose, placebo-controlled studies. In all 3 studies, escitalopram showed statistically significant greater mean improvement compared to placebo on the Hamilton Anxiety Scale. Results from the relapse-prevention study showed that treatment with escitalopram at 20 mg/day significantly reduced the risk of relapse of GAD.

The most commonly observed adverse reactions in the placebo-controlled double-blind studies in adult escitalopram patients (incidence of approximately 5% or greater and approximately twice the incidence in placebo patients) were nausea, ejaculation disorder (primarily ejaculatory delay), insomnia, fatigue, decreased libido, and anorgasmia.

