8.3.5 Removal of Subjects From the Study

A subject may voluntarily withdraw or be withdrawn from the study at any time for reasons including, but not limited to, the following:

- Withdrawal of consent
- Use of non-permitted concurrent therapy
- Noncompliance with the study drug or study schedule
- Lost to follow-up
- Adverse event
- Investigator request
- Intercurrent illness
- Protocol deviation
- Pregnancy
- Sponsor request
- Lack of efficacy
- Due to the COVID-19 pandemic
- Death

Subjects who do not complete the study will not be replaced.

Subjects are free to withdraw from the study at any time without providing reason(s) for withdrawal and without prejudice to further treatment. The reason(s) for withdrawal will be documented in the electronic case report form (eCRF).

Subjects withdrawing from the study will be encouraged to complete the same final evaluations as subjects completing the study according to this protocol, particularly

CONFIDENTIAL

safety evaluations. The aim is to record data in the same way as for subjects who completed the study.

Subjects who withdraw early from the study should complete the End of Treatment Visit and enter the 1-week down taper period.

Subjects should be monitored for the following symptoms when discontinuing treatment: dysphoric mood, irritability, agitation, dizziness, sensory disturbances (eg, paresthesias such as electric shock sensations), anxiety, confusion, headache, lethargy, emotional lability, insomnia, and hypomania. A gradual reduction in dose rather than abrupt cessation is recommended, whenever possible.

Reasonable efforts will be made to contact subjects who are lost to follow-up (eg, 3 attempts to contact the subject by telephone/letter). These efforts must be documented in the subject's file.

The sponsor has the right to terminate the study at any time in case of serious adverse events (SAEs) or if special circumstances concerning the investigational product or the company itself occur, making further treatment of subjects impossible. In this event, the investigator(s) will be informed of the reason for study termination.

Pregnancy

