11.6.1.1 Adverse Events

AEs will be coded to an SOC and PT using the latest available version of MedDRA. An AE (classified by PT) not present before the date of the first dose of the double-blind treatment period or during the double-blind down taper period or that was present before the first dose but increased in severity or seriousness will be considered a TEAE. An AE that starts more than 30 days after the date of the last dose of double-blind investigational product will not be counted as a TEAE.

An AE that starts during the double-blind down taper period or that increases in severity or seriousness during the double-blind down taper period will be considered a newly emergent AE (NEAE). The NEAEs during the double-blind down taper period will be summarized by SOC, PT, and treatment group for all subjects who enter the double-blind down taper period.

CONFIDENTIAL

The number and percentage of subjects reporting TEAEs in each treatment group will be tabulated by SOC and PT; by SOC, PT, and severity; and by SOC, PT, and causal relationship to the investigational product. If more than one AE is coded to the same PT for the same subject, the subject will be counted only once for that PT using the most severe and most related occurrence for the summarization by severity and by causal relationship to the investigational product, respectively.

The distribution of TEAEs by severity and causal relationship to the investigational product will be summarized by treatment group. The incidence of common ($\geq 2\%$ of subjects in any treatment group) TEAEs during the double-blind treatment period will be summarized by PT and treatment group.

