10.1 ADVERSE EVENTS

Adverse events will be coded by SOC and PT using the MedDRA version 22.0 or newer.

An AE (classified by PT) that occurs during the double-blind acute treatment period, during the down-taper period, or within 30 days after the date of the last dose of double-blind investigational product will be considered a treatment-emergent adverse event (TEAE) if it was not present before the date of the first dose of double-blind investigational product, or was present before the date of the first dose of double-blind investigational product and increased in severity during the double-blind acute treatment period or during the down-taper period, respectively.

If more than 1 AE was reported before the date of the first dose of double-blind investigational product and coded to the same preferred term, the AE with the greatest severity will be used as the benchmark for comparison with the AEs occurring during the double-blind acute treatment period or during the down-taper period that were also coded to that preferred term. An AE that occurs more than 30 days after the date of the last dose of double-blind investigational product in the study will not be counted as a TEAE but will be included in the listings.

Page 31 of 53

An AE occurring during the down-taper period or safety follow-up period will be considered a newly emergent AE (NEAE) if it is not present before the start of the down-taper period or was present before the start of the down-taper period but increased in severity during the down-taper period. All NEAEs will be summarized by SOC, PT, and treatment group.

The number and percentage of subjects in each treatment group reporting TEAEs during the double-blind acute treatment period will be tabulated by SOC and PT; by SOC, PT, and severity; and by SOC, PT, and causal relationship to the investigational product. If more than one AE is coded to the same PT for the same subject, the subject will be counted only once for that PT using the most severe and most related occurrence for the summarization by severity and by causal relationship to the investigational product, respectively. Study-treatment-related TEAEs are defined as TEAEs with relationship to treatment categorized as Possible, Probable, Very, Like/Certain or missing.

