16.9 CHARACTER VALUES OF CLINICAL LABORATORY PARAMETERS

If the reported value of a clinical laboratory parameter cannot be used in a statistical summary table because, for example, a character string is reported for a parameter of the numeric type, a coded value must be appropriately determined for use in the statistical analyses. The actual values, as reported in the database will be presented in the data listings.

Table 16.9–1 shows examples of how some possible laboratory results should be coded for analysis.

Page 49 of 53

Table 16.9–1. Examples of Coding Special Character Values for Clinical Laboratory Parameters

Laboratory Test, SI Unit	Possible Laboratory Results	Coded Value for Analysis
CHEMISTRY		 
ALT, U/L	< 5	5
AST, U/L	< 5	5
Bilirubin, total, μmol/L	< 2	2
URINALYSIS		
	< 2.775, Negative	0
	[2.775, 5.55)	1+
C1	[5.55, 13.875)	2+
Glucose, mmol/L	[13.875, 27.75)	3+
	[27.75, 55.5)	4+
	≥ 55.5	5+
141/T	$> 0.444, \ge 0.444, >0$, Trace	Positive
ketones, mmol/L	≤ 0, Negative	Negative
pH	> 8.0, ≥ 8.0	8.0
	≥ 8.5	8.5
	< 0, Negative	Negative
	[0, 0.15), Trace	0
Dustain a/I	[0.15, 0.3)	1+
Protein, g/L	[0.30, 1.0)	2+
	[1.0, 5.0)	3+
	>= 5.0	4+

ALT = alanine aminotransferase; AST = aspartate aminotransferase; SI = Le Système International d'Unités (International System of Units).

SAP SCT-MD-60 Allergan

Page 50 of 53

17.0 CHANGES TO ANALYSES SPECIFIED IN PROTOCOL

Only the following changes have been made to the protocol version 3.0: 30 Jun 2020.

Per protocol section 11.3, demographic parameters to be summarized include weight z-score and height z-score. However, these will be listed but not summarized.

No other changes have been made to the analyses specified in the protocol.

Page 51 of 53

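### The SAP's newly emergent AE rule adds a prior-presence condition that the protocol does not have, so an event that resolved on treatment and recurs on stopping at equal or lower severity may go uncounted

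*SAP*

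**What the plan says.** Protocol 11.6.1.1 sets two routes to a newly emergent AE (NEAE): "An AE that starts during the double-blind down taper period or that increases in severity or seriousness during the double-blind down taper period". It puts no condition on the subject's earlier history.

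SAP 10.1 starts from a wider window, "An AE occurring during the down-taper period or safety follow-up period", and then narrows what counts within it. Such an event "will be considered a newly emergent AE (NEAE) if it is not present before the start of the down-taper period", or if it "was present before the start of the down-taper period but increased in severity during the down-taper period". Seriousness is no longer a route.

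SAP 17.0 lists one change from the protocol, on the weight and height z-score summaries, and then states: "No other changes have been made to the analyses specified in the protocol".

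Two other places bear on the point. Protocol 8.3.5 lists symptoms to watch for on discontinuation, including "anxiety, confusion, headache, lethargy, emotional lability, insomnia, and hypomania". Protocol Section 6 says that the common adverse reactions in adult escitalopram studies, at about 5% or more and about twice placebo, "were nausea, ejaculation disorder (primarily ejaculatory delay), insomnia, fatigue" and others. Insomnia is on both lists.

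**The concern.** The NEAE table is the planned summary of what happens when the drug is withdrawn. Some discontinuation symptoms are also early side effects, so the same preferred term can be reported in the first weeks, resolve, and return on stopping. The protocol counts that return because it starts in the taper. The SAP may not, because the term had been present before.

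The excluded event has no other term-level home. The SAP's TEAE tables by system organ class and preferred term cover the acute treatment period only. The taper-period summaries of SAEs and of AEs leading to discontinuation pick up only events that meet those criteria. A mild, non-serious recurrence would be visible only in listings.

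If earlier episodes are more frequent on escitalopram, the condition removes more taper events from that arm and shrinks the between-arm difference in discontinuation effects.

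There is also an inconsistency within the SAP sentence. It opens the window to follow-up but counts worsening only during the taper. Subjects on 20 mg/day are still receiving 10 mg/day in Week 9, so their final dose comes at the end of the taper. A pre-existing term that worsens after that dose is not counted.

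**Working it through.** **Step 1: compare the rules by type of event.**

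| Event | Protocol 11.6.1.1 | SAP 10.1 |
|---|---|---|
| First onset in taper | counted | counted |
| First onset in follow-up | not counted | counted |
| Ongoing, more severe in taper | counted | counted |
| Ongoing, more serious but not more severe in taper | counted | not counted |
| Resolved earlier, recurs in taper, more severe | counted | counted |
| Resolved earlier, recurs in taper, equal or lower severity | counted | depends on *present before* |
| Present earlier, worsens in follow-up | not counted | not counted as worsening |

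**Step 2: what *present before* means.** The NEAE sentence does not say whether it means ongoing at taper start or reported at any earlier time. The TEAE rule in the same section uses parallel wording about the first dose. It classifies by preferred term and takes the most severe earlier report of that term as the benchmark, without requiring that report to be ongoing. Carried over to NEAEs, this gives the any-earlier-time reading.

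**Step 3: illustrate the loss for one preferred term under that reading.** The documents give no paediatric incidence and no taper recurrence rate, so every input is an assumption. Let *a* be the share of subjects with an earlier episode and *r* the true taper-onset risk. All earlier episodes are taken as resolved and no recurrence as more severe, which makes the loss as large as it can be for given *a* and *r*.

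- Independence: counted = *r*(1 − *a*).
- Odds ratio 3: with *x* the risk in subjects without an earlier episode, the risk in those with one is 3*x*/(1 + 2*x*). Solve *a*·3*x*/(1 + 2*x*) + (1 − *a*)*x* = *r*. Counted = (1 − *a*)*x*.

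Taper onset is 10% on escitalopram and 5% on placebo throughout, a true difference of 5.0 points.

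| Earlier incidence | Model | Counted, escitalopram | Counted, placebo | Difference |
|---|---|---|---|---|
| 20% vs 10% | independent | 10 × 0.80 = 8.0% | 5 × 0.90 = 4.5% | 3.5 |
| 20% vs 10% | odds ratio 3 | 0.80 × 7.57 = 6.1% | 0.90 × 4.25 = 3.8% | 2.2 |
| 5% vs 2.5% | independent | 10 × 0.95 = 9.5% | 5 × 0.975 = 4.9% | 4.6 |
| 5% vs 2.5% | odds ratio 3 | 0.95 × 9.29 = 8.8% | 0.975 × 4.79 = 4.7% | 4.2 |

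In the second row about 39% of escitalopram events and 24% of placebo events are lost. The lower pair of incidences follows the only anchor in the documents, the adult figure in Protocol Section 6.

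**Step 4: in subjects.** Take about 110 per arm entering the taper (128 × 0.86, an assumption, since early withdrawers should also enter it). The independent 20% vs 10% case loses 110 × 0.10 × 0.20 = 2.2 subjects on escitalopram and 110 × 0.05 × 0.10 = 0.55 on placebo. The independent 5% vs 2.5% case loses 0.55 and 0.14.

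**Step 5: boundary case.** With equal earlier incidence and equal taper risk the loss is equal in both arms, and no bias arises.

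**The case against.** The strongest reply is that the SAP sentence can be read as ongoing at taper start. Resolved episodes that recur are then counted under both documents and nothing is lost. The preferred-term classification and the severity benchmark are written for TEAEs against the first-dose date, and they are not repeated for NEAEs. This stands as a limit: the loss follows from the more natural reading, not from an explicit rule. It does not remove the need to say which reading applies.

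A reader might infer that the SAP discards recurring discontinuation symptoms generally, and more so on escitalopram. The documents do not support that. Recurrences at higher severity count under either reading. The on-drug list that includes insomnia is from adults, and nothing gives the frequency of recurrence by arm in this population. The SAP also adds the follow-up period, so first-onset events after the last dose are NEAEs under the SAP but not under the protocol. That works partly in the other direction, and the net effect is unknown.

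The limit on worsening is not a departure from the protocol, which confines worsening to the taper in the same way.

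A bare onset-date rule would create its own error. Protocol 10.1.2.2 requires each change in severity to be recorded as a separate event, so an AE that eases from severe to mild in the taper could generate a record dated in the taper and be miscounted as new. The repair has to deal with this.

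Finally, safety is analysed descriptively, and taper SAEs and AEs leading to discontinuation are summarised regardless of NEAE status. That limits the consequence.

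**Conclusion.** The two definitions differ, cannot both be followed, and the difference is not declared in SAP 17.0. On the reading that the SAP's own TEAE rule suggests, one class of event is left out: resolved on treatment, recurring on stopping under the same preferred term, at equal or lower severity, not serious and not leading to discontinuation.

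Attenuation of the arm difference is plausible for insomnia but not shown for this population. Under the assumed rates, a 5.0-point difference falls to between 2.2 and 4.6 points. The lower end needs on-treatment incidences well above the adult anchor together with a strong link between earlier episodes and recurrence. At the anchor, the loss is about half a point to one point and often less than one subject per term. If *present before* means ongoing, these recurrences are not lost.

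The follow-up point is a separate and smaller inconsistency inside the SAP. Both are worth correcting before the blind is broken, because the table concerned is the planned term-level summary of discontinuation effects.

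**What to change.** Amend SAP 10.1 as follows.

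- Count as an NEAE any new episode with onset after the end of the acute treatment period and through the safety follow-up, even if an earlier, resolved episode of the same preferred term exists.
- Exclude episodes ongoing at taper start unless they worsen.
- Treat a record created only because severity decreased as a continuation of the earlier event, not as a new onset.
- Apply the worsening criterion through follow-up, to match the window that the sentence opens.
- In SAP 17.0, list every difference from Protocol 11.6.1.1 that remains, including the follow-up window and the role of seriousness.

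The cost is a few sentences and a revised derivation of the AE flag. NEAE counts will be slightly higher, and programming must identify AE records that belong to one episode so that severity step-downs are not counted.

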10.1.2.2 Adverse Events

Adverse Event Definition

An AE is defined as any untoward medical occurrence in a clinical study subject administered a medicinal product which does not necessarily have a causal relationship with this treatment. An AE can therefore be any unfavorable and unintended sign (including an abnormal laboratory finding), symptom, or disease temporally associated with the use of a medicinal (investigational) product, whether or not it is related to the medicinal (investigational) product. This includes an exacerbation of pre-existing conditions or events, intercurrent illnesses, drug interaction or the significant worsening of the indication under investigation that is not recorded elsewhere in the eCRF under specific efficacy assessments. Anticipated fluctuations of pre-existing conditions, including the disease under study that do not represent a clinically significant exacerbation or worsening need not be considered AEs.

It is the responsibility of the investigator to document all AEs that occur during the study. AEs will be elicited by asking the subject a nonleading question, for example, "Have you experienced any new or changed symptoms since we last asked/since your last visit?". AEs should be reported on the appropriate page of the eCRF.

CONFIDENTIAL

Assessment of Severity

Each AE will be assigned a category by the investigator as follows:

Mild: An AE that is easily tolerated by the subject, causes minimal discomfort and does not interfere with everyday activities.

Moderate: An AE that is sufficiently discomforting to interfere with normal everyday activities; intervention may be needed.

Severe: An AE that prevents normal everyday activities; treatment or other intervention usually needed.

If there is a change in severity of an AE, it must be recorded as a separate event.

Assessment of Causality

Every effort will be made by the investigator to assess the relationship of the AE, if any, to the study drug. Causality should be assessed using the categories presented in the following table:

Unrelated: Clinical event with an incompatible time relationship to study drug administration, and that could be explained by underlying disease or other drugs or chemicals or is incontrovertibly not related to the study drug.

Unlikely: Clinical event whose time relationship to study drug administration makes a causal connection improbable, but that could plausibly be explained by underlying disease or other drugs or chemicals.

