Possible: Clinical event with a reasonable time relationship to study drug administration, but that could also be explained by concurrent disease or other drugs or chemicals.

Probable: Clinical event with a reasonable time relationship to study drug administration, and is unlikely to be attributed to concurrent disease or other drugs or chemicals.

Very Likely/Certain: Clinical event with plausible time relationship to study drug administration, and that cannot be explained by concurrent disease or other drugs or chemicals.

Action Taken

The investigator will describe the action taken in the appropriate section of the eCRF, as follows:

- None
- Study drug stopped

CONFIDENTIAL

- Study drug temporarily interrupted
- Concomitant medication
- Other, specify.

Follow-up of Adverse Events

All investigators should follow up subjects with AEs until the event is resolved or until, in the opinion of the investigator, the event is stabilized or determined to be chronic. Details of AE resolution must be documented in the eCRF.

Documentation and Reporting of Adverse Events

All AEs from the signing of the informed consent form (ICF) until 30 days after receiving the last dose of study drug will be collected according to the procedures outlined above at the timepoints specified in the Schedule of Assessments ([Section 8.1.2/8.1.3](#)), and as observed or reported spontaneously by study participants.

AEs should be reported and documented in accordance with the procedures outlined below. All AEs occurring during the study must be documented on the relevant eCRF pages. The following data should be documented for each AE:

- Description of the symptom event
- Classification of 'serious' or 'not serious'
- Severity
- Date of first occurrence and date of resolution (if applicable)
- Action taken
- Causal relationship
- Outcome of event (unknown, recovered, recovering, not yet recovered, recovered with sequelae, death [with date and cause reported]).

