Within 24 hours of learning of any AE that meets one of the criteria for an SAE, the study center personnel must report the event to Global Drug Safety on the SAE Form for Clinical Trials. The medical director may also be notified by telephone, however, notification of the medical director by telephone does not substitute for reporting of the event to the sponsor by email/fax of the SAE form for Clinical Trials within the required time period.

If, during follow-up, any nonserious AE worsens and eventually meets the criteria for an SAE, that AE should be recorded as a new SAE.

The study center must transmit the SAE Form for Clinical Trials to the SAE email address or fax number shown below. Even if an initial report is made by telephone, the SAE Form for Clinical Trials completed with all available details must still be faxed or emailed within 24 hours of knowledge of the event at the study center.

Supplemental information should be submitted as soon as available and may include laboratory results, radiology reports, progress notes, hospital admission and emergency

CONFIDENTIAL

room notes, holding and observation notes, discharge summaries, autopsy reports, and death certificates.

The investigator is expected to take all therapeutic measures necessary for resolution of the SAE. Any medications or procedures necessary for treatment of the SAE must be recorded on the appropriate pages of the subject's eCRF. All SAEs are to be followed by the study staff until resolution or until the SAE is deemed stable. *The sponsor may contact the study center to solicit additional information or follow up on the event.*

Fax or email the SAE Form for Clinical Trials to the following SAE fax number/email address:

[contact] (back-up [contact])
Email: [contact]

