The distribution of TEAEs by severity and causal relationship to the investigational product will be summarized by treatment group. The incidence of common ($\geq 2\%$ of subjects in any treatment group) TEAEs during the double-blind acute treatment period will be summarized by PT and treatment group.

A serious adverse event (SAE) that occurred between the date of the first dose of double-blind investigational product and 30 days after the date of the last dose of double-blind investigational product in the study, inclusive, will be considered an on-therapy SAE. The incidence of SAEs and AEs leading to premature discontinuation of the study will also be summarized by study period (separately for double-blind acute treatment period and double-blind down taper period), SOC, PT, and treatment group.

The above summaries will be sorted by decreasing frequency of SOC and by the decreasing frequency of PT within SOC for the escitalopram treatment group. If incidence for more than 1 term is identical, they will then be sorted alphabetically. In addition, the above summaries will be presented as all AEs, AEs that are associated with the COVID-19 pandemic (as determined by the investigator), and AEs that are not associated with the COVID-19 pandemic. AEs associated with the COVID-19 pandemic will be listed separately.

Listings will be presented for subjects with SAEs, subjects with AEs leading to premature discontinuation, and subjects who died for the Screened Population. All subjects with SAEs, including those reported during the screening period or more than 30 days after the date of the last dose of the double-blind investigational product, and subjects discontinuing due to AEs before the start of double-blind investigational product will be included in these listings

Page 32 of 53

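### SAP 10.1 opens the newly emergent AE definition to follow-up but counts worsening only in the taper; the TEAE rule has the same gap, and SAP 17.0 does not declare the departure from the protocol

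*SAP*

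**What the plan says.** SAP 10.1 defines the NEAE in one sentence, which opens on two periods: "An AE occurring during the down-taper period or safety follow-up period will be considered a newly emergent AE (NEAE". An event then qualifies in one of two ways: it was absent before the taper, or it "was present before the start of the down-taper period but increased in severity during the down-taper period". The SAP does not define the follow-up period named there. All NEAEs go into one table by system organ class (SOC), PT and treatment group.

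The TEAE rule in the same section classifies events by PT and runs to 30 days after the last dose. Its worsening limb counts an increase in severity only in the acute or taper period. The sentence that sets the pre-dose severity benchmark names the same two periods.

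The other SOC/PT tables in SAP 10.1 are bounded in time. The TEAE tables count subjects "reporting TEAEs during the double-blind acute treatment period will be tabulated by SOC and PT". SAEs and AEs leading to discontinuation are summarized "separately for double-blind acute treatment period and double-blind down taper period".

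Protocol 11.6.1.1 words the NEAE differently: "An AE that starts during the double-blind down taper period or that increases in severity or seriousness during the double-blind down taper period". Protocol 10.1.2.2 says that AEs from consent "until 30 days after receiving the last dose of study drug will be collected", and adds: "If there is a change in severity of an AE, it must be recorded as a separate event". Under protocol 10.1.2.2.1, if "any nonserious AE worsens and eventually meets the criteria for an SAE, that AE should be recorded as a new SAE". SAP 17.0 lists one change from the protocol, on weight and height z-scores, and says there is no other.

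**The concern.** The opening of the NEAE sentence and its worsening limb cover different periods, and no reason is given. Protocol 11.6.1.1 limits both limbs to the taper and so agrees with itself. The SAP added follow-up to the onset limb only, which looks like an incomplete edit.

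Safety is part of the primary objective, and the NEAE table is where effects of stopping the drug should show. Under protocol 8.4.1, subjects on 20 mg/day take 10 mg/day in Week 9. On the nominal schedule they are first off drug in follow-up, the period in which worsening is not counted. Protocol 8.3.5 lists discontinuation symptoms to watch for, among them agitation, insomnia and headache. If one of these was recorded as an AE on treatment and became worse once the drug was stopped, the table would not show the worsening.

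**Working it through.** The plan gives no figure to reproduce. The check is to take each course that an event can follow and apply the SAP rules to it, with presence judged by PT and follow-up taken to end no later than 30 days after the last dose.

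| Course of the PT | NEAE (SAP 10.1) | TEAE (SAP 10.1) |
|---|---|---|
| A. First seen in follow-up | Yes, new | Yes, new |
| B. Began in the acute period, worsens in the taper | Yes, worsened | Yes, from onset |
| C. Began in the acute period, worsens only in follow-up | **No** | Yes, from onset |
| D. Present before first dose, worsens in the taper | Yes, worsened | Yes, worsened |
| E. Present before first dose, worsens only in follow-up | **No** | **No** |

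**Course C** is left out of the NEAE table, although course A on the same calendar day is in it. The subject already appears under that PT in the acute TEAE tables, so what is lost is the later step in severity.

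**Course E** is in neither class. The worsening is recorded as a separate event and collected, but neither rule picks it up for a table.

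**Against the protocol.** On NEAEs, protocol 11.6.1.1 is narrower than the SAP in time (taper only, so course A is not an NEAE) and wider in kind (severity or seriousness; the SAP counts severity alone). Its TEAE sentence, read literally, also counts seriousness and sets no period for the increase, so course E could be a TEAE there. SAP 17.0 mentions none of this.

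**Time covered by the worsening limb.** The taper lasts 7 days, and the Week 10 call falls 7 days later on the nominal schedule.

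- Follow-up ends at the Week 10 call: 7 / (7 + 7) = 7/14 = 50%.
- Follow-up runs to 30 days after the last dose: 7 / (7 + 30) = 7/37 = 18.9%.

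These are shares of calendar time, not of events. The documents give no rate for such worsening, so the number of affected subjects cannot be stated. As a scale: if all 128 planned subjects in an arm entered the taper, each omitted subject would change a PT row by 1/128 = 0.8 percentage points.

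**The case against.** **The by-PT reading is not stated for NEAEs.** The SAP says that TEAEs are classified by PT and does not repeat this for NEAEs. Protocol 10.1.2.2 makes each change in severity a separate record, so event by event a worsening in follow-up is new and is counted. But on that reading every worsening is a new event, and the worsening limb has no work to do. One can reply that protocol 11.6.1.1 carries the same overlap. The by-PT reading therefore remains the likelier one, not a certain one. If two programmers could read it differently, the clause still needs settling, and SAP 17.0 is inaccurate on either reading.

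**Most affected subjects are already tabulated.** This stands for course C. In addition, the SAP 10.1 summary of TEAEs by severity and causality names no period and might show the later severity. It does not help course E, which is not a TEAE.

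**Dropping seriousness matters little.** This largely stands: an event that becomes serious is recorded as a new SAE, SAEs within 30 days of the last dose are classed as on-therapy, and all SAEs are listed. The difference from the protocol is still undeclared.

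**Returning to the protocol's taper-only rule would also remove the mismatch within the NEAE sentence.** It would, but course A would then leave the NEAE table, and with it the first off-drug period of the 20 mg/day subjects.

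**A reader might infer that ordinary GAD symptoms that worsen off drug go uncounted.** The documents do not support that. The worsening limb concerns events already recorded as AEs before the taper. Protocol 10.1.2.2 does not require anticipated fluctuation of the disease under study to be an AE. A baseline symptom that first worsens to a clinically significant degree in follow-up would normally be first recorded then, and the onset limb would count it.

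**Conclusion.** The gap is real and narrow. By PT, an AE recorded before the taper that worsens only in follow-up is not an NEAE. If it was also present before the first dose, it is not a TEAE either. No other SOC/PT table in SAP 10.1 clearly shows the worsening. The SAP's NEAE rule also differs from protocol 11.6.1.1 in period and in the treatment of seriousness, without a declaration in SAP 17.0.

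The effect is confined to descriptive safety tables. The data are collected to 30 days after the last dose, AEs that began on treatment are already TEAEs, and no efficacy inference changes. The conclusion rests on the by-PT reading; the size beyond calendar time is unknown.

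A reader might also infer that the Week 10 call lacks a required C-SSRS. It does not. Protocol 8.2.1 places that scale at study visits, Week 10 is a telephone contact, and protocol 10.1.2.1 requires continual evaluation of suicidality risk throughout participation.

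**What to change.** Change SAP 10.1 before unblinding:

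1. NEAE: let the worsening limb cover an increase in severity or seriousness in the taper or in safety follow-up.
2. Define safety follow-up as running from the end of the taper to 30 days after the last dose, which matches AE collection.
3. TEAE: extend the worsening limb to 30 days after the last dose in the same way, and extend the benchmark sentence to match. Changing the NEAE rule alone would make course E an NEAE but not a TEAE.
4. State that presence before the taper is judged by PT.
5. Declare the NEAE and TEAE changes in SAP 17.0.

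The cost is a few clauses, one definition, an entry in SAP 17.0 and the matching program flags. No new data are needed. The SAP 17.0 entry is enough if the protocol is not otherwise being amended; if it is, section 11.6.1.1 should be brought into line.
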